assigned to one of two study conditions (intervention or control). Participants at all four collaborating transplant centers will be seen by providers who utilize T-REX, thus allowing us to test the independent effect of individual-level education on a systems-level intervention. The primary outcome is the percent of patients with at least one living donor inquiry. Secondary outcomes will test the effect of the intervention on key constructs of the Information-Motivation-Behavioral Skills model to determine possible mediating pathways. Participants will undergo baseline assessment, access either the intervention or control educational materials, and complete an immediate follow-up assessment. Living donor inquiries will be examined over the subsequent 12 months. The process evaluation will utilize transplant center administrative records, immediate follow-up data from participants, website usage statistics, and study records. It is anticipated that achievement of these aims will yield outcomes with great clinical and public health impact.

Our specific aims are to:

- **Aim 1: To develop and refine a web-based version of Living ACTS. We will adapt our existing intervention for an online environment.** A series of individual interviews with 10 participants will be conducted to obtain feedback on the web-based version of Living ACTS. Participant feedback will be used to refine and finalize the web-based intervention
- **Aim 2: To conduct an outcome evaluation of the newly created web-based Living ACTS intervention by comparing the percent of patients with at least one inquiry from a potential living donor among patients who receive Living ACTS to those who receive a control website with an embedded educational video.** Patients who start the transplant evaluation at four transplant centers will be assigned to intervention (systems + individual intervention) or control (systems intervention alone).

H₁: A greater proportion of participants who receive a culturally-sensitive website with embedded video (Living ACTS) will have at least one living donor inquiry over the subsequent 12 months than control participants who received standard education.

H₂: Patients in the intervention (vs. control) group will have a significantly greater increase in knowledge, motivation, and self-efficacy for the behavioral skills to initiate a conversation about LDKT with family or friends from baseline to immediate follow-up

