- **Aim 2: To conduct an outcome evaluation of the newly created web-based Living ACTS intervention by comparing the percent of patients with at least one inquiry from a potential living donor among patients who receive Living ACTS to those who receive a control website with an embedded educational video.** Patients who start the transplant evaluation at four transplant centers will be assigned to intervention (systems + individual intervention) or control (systems intervention alone). We hypothesize that intervention patients will have significantly more living donor inquiries than control participants over the subsequent 12 months. Secondary analyses will explore the effect of the intervention on information, motivation, and self-efficacy for the behavioral skills to discuss LDKT with others.
- **Aim 3: To conduct a process evaluation of the newly created web-based Living ACTS intervention by adapting commonly used process evaluation constructs (context, reach, dose received, fidelity, and recruitment) for an online environment.** We will collect data from participants, transplant center records, study records, and Google Analytics to inform process evaluation findings.

C. Study Designs and Methods

C.1. Overview

The study seeks to fulfill the following specific aims by conducting a scientifically rigorous RCT among 850 AA ESRD patients presenting for KT evaluation at a transplant center:

1. *To develop and refine a web-based version of Living ACTS*
2. *To conduct an outcome evaluation of the newly created web-based Living ACTS intervention by comparing the percent of patients with at least one inquiry from a potential living donor among patients who receive Living ACTS to those who receive a control website with an embedded educational video*
3. *To conduct a process evaluation of the newly created web-based Living ACTS intervention by adapting commonly used process evaluation constructs (reach, recruitment, fidelity, dose delivered, dose received, and context) for an online environment*

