To complete aim 1, we will contract with Tomorrow Pictures and Emory Web Services to create the Living ACTS website and embed the current Living ACTS video. We will conduct a series of individual interviews (10 total) to gain feedback on the website from individuals meeting our participant demographic profile. Participant feedback will be used to refine and finalize the intervention website. Next, the multi-center trial will collect data from 850 AA ESRD patients who have been referred for evaluation at one of four participating transplant centers in the Southeast. The proposed methods were designed to maximize the robustness of the data while minimizing bias in study design, methodology, analysis, interpretation, and reporting. Random assignment to condition (also for Aim 2) reduces the chances of initial group differences in maturational rates, historical events, and regression artifacts.⁶² Additionally treating the two groups equivalently in terms of attention to a website with embedded video, data collection methods, and instrumentation improve internal validity by minimizing testing and instrumentation effects.⁶²

Patients will be enrolled into the study through a Zoom video call or telephone call before or after their second day of evaluation at which point they will be consented verbally and undergo baseline assessment. Next, they will be randomized to condition, access either the intervention or control website, and complete an immediate follow-up assessment. Living donor inquiries will be tracked using administrative data from the transplant centers for the subsequent 12 months. Aim 3 will be achieved through the analysis of transplant center data (for context and reach), web-site usage statistics (for fidelity), study records (for recruitment), and patient-level data (for dose received). We are intentionally not testing the effect of T-REX given its alignment with the recommendations generated by the Consensus Conference on Best Practices in Live Kidney Donation.⁶³ This study is uniquely designed to isolate the effect of the individual-level intervention within a system-level intervention to determine its added value.

C.2. Preliminary Studies

C.2.1. The RaDIANT (Reducing Disparities In Access to kidNEY Transplantation)

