Through the Powerchart system, the project coordinator will review the schedule for the transplant center of all patients who will have or had an evaluation appointment during a 7 – 10 day period before or after the scheduled appointment. The coordinator will not have a relationship or familiarity with these patients prior to screening them for eligibility. The project coordinator will also review some key patient demographics (race, sex, age, and BMI) to ensure eligibility for the study. Additionally, access to patient clinical charts will be accessed via Powerchart to confirm patient eligibility (i.e. transplant status, ESRD status, and additional eligibility criteria). The project coordinator will obtain the patient's telephone number from Powerchart to call the patient to ask the patient to participate in the study. If the patient is willing to participate, the project coordinator will obtain the patient's email address to send the appropriate Zoom video call information, appointment time and date. The patient will be scheduled for a Zoom video call no later than a week from the initial phone call. The project coordinator will also call the patient one day before the scheduled Zoom video call to confirm the appointment with the patient. If the patient does not have zoom capabilities, the coordinator will set up a video call with the patient. The coordinator will also have the option to recruit a patient in-person at the transplant clinic. Data collectors will maintain all necessary clearances and perform required trainings to gain and maintain access to electronic medical records. Project coordinators will be rigorously trained on how to recruit and screen patients for study eligibility.

Eligibility Criteria. All patients referred (from dialysis facility, chronic kidney disease clinic, or self) and scheduled for an evaluation at one of the four study sites within the study time period. Our screening process will be based on information gathered from either their referral form or electronic medical record and ensure that patients are:

- (1) AA or Black
- (2) age 18 to 70 years
- (3) have BMI < 39
- (4) are English-speaking (Language eligibility will be confirmed by project coordinator during a telephone call with the patient prior to the Zoom video call)

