Proportion of study participants who have at least one living donor inquiry by friends/family of the patient over 12 months from baseline (evaluation start). This discrete outcome has been used in prior studies⁶⁹ and is a necessary step prior to LDKT. These data are currently captured for all patients as a discrete field from electronic medical record for each potential recipient. Inquiries are defined by all centers as a telephone inquiry to the transplant center's living donor (each center has a separate telephone line for this purpose). For each study site, a data collection form that captures potential recipient ID (i.e. study participant), date of living donor inquiry, and donor inquiry ID, will be securely obtained from each transplant center following a 12 month period from enrollment. Data will be collected electronically for all study participants through a secure, HIPAA-compliant data server (QualityNet) that all 4 transplant centers have used in prior SEKT Coalition studies^{53,70}.

Secondary Outcomes. Captured in the baseline and immediate follow-up survey, which will include measures of information, motivation, and behavioral skills that we have used in past research

- a. a 25-item assessment of knowledge and understanding of donation/transplantation^{60,71}
- b. a 9-item scale asking assessing motivation to ask a family member to be a living donor⁶⁰
- c. a 10-item behavioral skills scale that measures confidence in initiating a conversation about LDKT⁶⁰
- d. a 3-item behavioral intentions scale that measures intention to discuss LDKT with family members⁷²
- e. a single-item measure of comfort in initiating conversation about LDKT⁷³
- f. several items measuring demographic characteristics (age, gender, highest level of education)

Study Size Justification & Power Calculation.

Study Size Justification. There were an estimated 3,500 ESRD patients evaluated for transplantation, and 2,180 new additions to the waiting list in the four transplant center sites in 2015. The majority (61.9%) of the waitlisted patients were AA. Thus, we will have a pool of over 1400 potential study participants over the four study sites over 1 year, which will ensure we will meet our estimated sample size of n=850 AA ESRD patients (1:1 randomization). We expect that it is possible that ~25% of patients evaluated will not be eligible for transplant and thus will not have the opportunity to have LDKT, and these patients not be considered in main outcome analyses.

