Power Calculation for Primary Endpoint. Based on preliminary data showing that the proportion of AAs with ≥ 1 living donor inquiry is 12% at baseline, we have 80% power to detect a 7% difference between the intervention and control groups, accounting for potential correlation of patients within study sites (correlation on the same subject of 0.5), with $\alpha=0.05$. We expect little attrition in this trial, since follow-up data on the number of living donor inquiries will be obtained through medical record review. Based on our prior trial,⁹ we expect >90% participation.

Statistical Analysis Plan. We will initiate the analytical process by conducting basic descriptive statistics on all variables, examining continuous variables for normality, and exploring the Cronbach's alpha for relevant scales.

- Our main analyses seek to answer the following hypothesis:

H₁: A greater proportion of participants who receive a culturally-sensitive website with embedded video (Living ACTS) will have at least one living donor inquiry over the subsequent 12 months than control participants who received standard education.

- Our secondary analyses seek to answer the following hypothesis:

H₂: Patients in the intervention (vs. control) group will have a significantly greater increase in knowledge, motivation, and self-efficacy for the behavioral skills to initiate a conversation about LDKT with family or friends from baseline to immediate follow-up

To ensure adequate balance across study arms, baseline covariates will be compared using Student *t* tests and χ^2 tests, as appropriate. Variables found to have significant differences ($p <0.05$) by study arm will be

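### The 12-month window for the primary outcome is written to start at evaluation start, which is not the date of randomisation

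*Combined protocol and SAP*

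**What the plan says.** The Primary Outcome paragraph (C.4) gives the definition: at least one "living donor inquiry by friends/family of the patient over 12 months from baseline (evaluation start"). Later in that paragraph, the form carrying participant ID, inquiry date and donor inquiry ID "will be securely obtained from each transplant center following a 12 month period from enrollment".

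Other places put the 12 months after the study session:
- Opening summary: "Living donor inquiries will be examined over the subsequent 12 months", listed after baseline, the website and the immediate follow-up.
- Objectives, Aim 2: "intervention patients will have significantly more living donor inquiries than control participants over the subsequent 12 months".
- C.1 Overview: "Living donor inquiries will be tracked using administrative data from the transplant centers for the subsequent 12 months".
- H1 in the Statistical Analysis Plan: more intervention participants "will have at least one living donor inquiry over the subsequent 12 months than control participants who received standard education".

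The list of outcome variables and the description of the mixed model give a 12-month length with no starting point. Table 2 describes the call but does not date it.

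On the timing of enrolment, C.1 has patients join by Zoom or telephone "before or after their second day of evaluation at which point they will be consented verbally and undergo baseline assessment". Patient Recruitment Methods has the coordinator review the schedule over a 7 to 10 "day period before or after the scheduled appointment", with the Zoom call no more than a week after the first phone call and in-person recruitment as an option. Randomization follows directly on consent and the baseline measures, and the Time paragraph allows 1 hour 30 minutes for the whole session.

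**The concern.** Consent, baseline survey, randomisation, website viewing and immediate follow-up form one short session. Baseline, enrolment and the start of the following 12 months are therefore in practice one date, that of randomisation. Evaluation start is a different date: the session can fall on either side of the evaluation, and C.1 ties it to the second evaluation day.

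If the definition is applied as written, two things follow. A patient randomised after evaluation start can be counted for an inquiry the website could not have caused, and loses the same number of days at the end of the 12 months. A patient randomised before evaluation start has the first days after viewing the website left out. No rule says what to do with an inquiry dated before randomisation.

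This is the primary outcome, and its starting point should not be open to choice once inquiry data have been seen.

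**Working it through.** **Inputs.** Total 850, allocated 1:1, so 425 per arm (Study Size Justification). Control proportion 12%, difference 7 points, 80% power, α = 0.05 (Power Calculation for Primary Endpoint).

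**Assumptions.** Two-sided test (sidedness is not stated). The 12%, described as a baseline figure with no period given, is a 12-month control rate. First inquiries are spread evenly over 365 days. The website multiplies only inquiries after randomisation, by 19/12.

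**Step 1: the plan's own figure.** With p₁ = 0.12, p₂ = 0.19, p̄ = 0.155, n = 425:

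power = Φ{[(p₂ − p₁) − 1.96·√(2p̄(1 − p̄)/n)] / √([p₁(1 − p₁) + p₂(1 − p₂)]/n)}

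= Φ{[0.07 − 1.96 × 0.02483] / 0.02471} = Φ(0.864) = 80.6%.

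This agrees with the stated 80%. It uses all 850 patients and makes no adjustment for site correlation.

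**Step 2: what the literal window does.** If randomisation comes L days after evaluation start, the window takes in L days before randomisation and drops the last L of the 12 months after it. If randomisation comes L days before evaluation start, the first L days after randomisation are omitted.

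**Step 3: size when randomisation follows evaluation start.** The share of control inquirers falling before randomisation is f = L/365. The observed control rate stays at 0.12. The observed intervention rate is 0.12f + 0.12(1 − f) × 19/12. The expected number of pre-randomisation inquirers per arm is 425 × 0.12 × f.

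The plan does not state L. One reading of Patient Recruitment Methods is 10 days plus up to 7 days to the Zoom call, or 17 days. This is not a bound: the time from chart review to phone call is not limited, and in-person recruitment would shorten the lag. The 30-day row is an assumption, to show the range.

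| Patients and lag | f | Intervention rate | Difference | Pre-randomisation inquirers per arm | Power |
|---|---|---|---|---|---|
| Window from randomisation | 0 | 19.0% | 7.0 points | 0 | 80.6% |
| A quarter at 17 days, rest at 0 | 0.0116 | 18.9% | 6.9 | 0.6 | 79.8% |
| All at 7 days | 0.0192 | 18.9% | 6.9 | 1.0 | 79.2% |
| All at 10 days | 0.0274 | 18.8% | 6.8 | 1.4 | 78.6% |
| All at 17 days | 0.0466 | 18.7% | 6.7 | 2.4 | 77.1% |
| All at 30 days | 0.0822 | 18.4% | 6.4 | 4.2 | 74.2% |

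A constant-hazard model in place of an even spread gives 79.3%, 78.7% and 77.3% at 7, 10 and 17 days.

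**Step 4: size when randomisation precedes evaluation start.** At 10 days, 10/365 = 2.7% of 12-month inquirers are left out: 425 × 0.12 × 10/365 = 1.4 in the control arm and 425 × 0.19 × 10/365 = 2.2 in the intervention arm. Under an even spread the same expected numbers are picked up after month 12, so no power is lost.

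**Step 5: direction.** Inquiries before randomisation cannot depend on the arm. They are equal in expectation, pull the difference towards zero, and do not raise type I error.

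**The case against.** The strongest reply is that this is a slip of two words. The defining sentence itself says baseline, the data request runs from enrolment, and four other places put the 12 months after the session. On that reading the parenthesis is only a gloss. The Usual Care description supports it, since it has the control video watched in a private room during the scheduled evaluation; with in-clinic delivery, baseline and evaluation would nearly coincide. Lags can also run either way: with half of patients randomised 10 days after evaluation start and half 10 days before, power is 79.6% on the model above. And 17 days is built from limits that run from the scheduled appointment and from the first phone call, not clearly from evaluation start.

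Much of this stands. Enrolment may well be what the sponsor intended, the effect is small, and 17 days is only one reading. But the enrolment wording governs when data are obtained, not which inquiries count. In-clinic delivery does not make evaluation start the randomisation date when C.1 ties enrolment to the second evaluation day and allows it before or after. The parenthesis is also the only place that names a clinical event as the start of the outcome window, and a site or analyst following the definition would use it.

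A further fair point is that excluding earlier inquiries does not settle whether a repeat call after randomisation counts when that donor first called before it. The definition needs a line on this.

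**Conclusion.** The concern holds. As written, the primary-outcome window starts at an event that is not randomisation and can precede or follow it, and the rest of the plan points to a different start. The consequence is small: for lags of 7 to 17 days in every patient, about 1.0 to 2.4 pre-randomisation inquirers per 425 and a loss of about 1.4 to 3.5 points of power from 80.6%; less if lags are mixed. There is no favoured arm and no inflation of type I error.

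These figures rest on an even spread of inquiries and on lags the plan does not give. If inquiries cluster near evaluation start, dilution is larger: for illustration only, with 10% of control first inquirers before randomisation the intervention rate would be 18.3% and power 72.7%. The plan has no timing data to support or exclude that. The plan should make the change because it concerns the primary outcome and costs almost nothing.

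**What to change.** In the Primary Outcome paragraph, define the outcome as at least one living donor inquiry dated after randomisation and within 12 months of randomisation. Replace both the evaluation-start origin and the enrolment origin with randomisation. State that earlier inquiries do not count, that patients who had one stay in the denominator, and whether a later call from a donor who first called before randomisation counts; the donor inquiry ID makes that rule workable.

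Use the same origin in the opening summary, Objectives (Aim 2), C.1 and H1, and add it to the outcome list and the model description. Fix the rule before inquiry data are seen.

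The cost is wording and a date filter: inquiry date and participant ID are already on the form and can be linked to the randomisation date. Data must run to 12 months after randomisation, and the plan already waits 12 months from enrolment. The window is moved, not shortened, so under the assumptions above the expected control count stays at 425 × 0.12 = 51 and power at 80.6%. Sample size does not change.

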entered as covariates in subsequent analyses. We note that detected differences may be site-specific and will explore site stratifications if we observe differences. Multivariable modeling techniques will be employed, if necessary, to correct for lack of balance in demographic or clinical characteristics between the two groups. For the main outcome, we will use generalized linear mixed models (GLMMs) for adjusted analyses of the data, specifying the logit link function for the binary outcomes (i.e. at least one living donor inquiry over 12-month period). Treatment group will be the independent variable of primary interest, modeled as a fixed effect with the control group specified as reference group. We will also include fixed effects for any potential confounding covariates noted in bivariable analysis. A random intercept will be considered to increase generalizability of results. To control for potential contamination bias over the course of the study, we will consider controlling for time of study entry.

We will pursue a similar modeling technique as described above for secondary analyses except that change in each of the three dependent variables will be the continuous (vs. binary) outcomes. We will conduct exploratory analyses where we assess change in behavioral intentions and comfort in initiating conversations about LDKT as outcomes. All data will be analyzed by the program coordinator for the study at Emory University with the oversight of Drs. [name] and [name], who will be blinded to study allocation. SAS 9.3 (Cary, NC) will be used for all analyses.

C.5. Specific Aim 3: To conduct a process evaluation of the newly created web-based Living ACTS intervention by adapting commonly used process evaluation constructs (reach, recruitment, fidelity, dose delivered, dose received, and context) for an online environment In Table 3 we describe what data will be collected, how, and when. **Table 3.** Process evaluation components and measures (Linnan & Steckler, 2002)

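### Adjustment for a living donor inquiry before randomisation is not prespecified in the primary model, although the centres already record inquiries: a cheap improvement whose gain in power is uncertain

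*Combined protocol and SAP*

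**What the plan says.** All references are to section C.4 unless stated.

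- **Primary Outcome.** The endpoint is at least one living donor inquiry in 12 months, counted from baseline, which is glossed as the start of evaluation. On the source: "These data are currently captured for all patients as a discrete field from electronic medical record for each potential recipient". The form sent by each centre holds the recipient ID, the inquiry date and a donor inquiry ID. It is obtained 12 months after enrolment, and no look-back before enrolment is mentioned.
- **Power Calculation for Primary Endpoint.** Preliminary data are said to show that "the proportion of AAs with ≥ 1 living donor inquiry is 12% at baseline", and on that basis "we have 80% power to detect a 7% difference between the intervention and control groups".
- **Statistical Analysis Plan.** The primary model is a logit mixed model with arm as a fixed effect. Baseline variables that differ by arm at p<0.05 become covariates. In addition: "We will also include fixed effects for any potential confounding covariates noted in bivariable analysis". No covariate is named. A random intercept and time of study entry are only to be considered.
- **Elsewhere.** Prior inquiry is not among the listed survey measures, the eligibility criteria do not exclude patients who have one, and randomisation is simple 1:1 without stratification. The secondary outcomes, by contrast, are analysed as change from baseline.

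**The concern.** A patient who already has an interested donor may well be more likely to have an inquiry in the following year. If so, prior inquiry is a baseline predictor of the primary outcome, and adjusting for it sharpens the arm comparison and removes chance imbalance in that variable without extra patients or visits.

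The planned covariate rule is a poor way to capture this. A test of imbalance admits a variable because of how the allocation fell, not because it predicts the outcome. Under simple randomisation any true baseline variable passes a p<0.05 screen about 5% of the time, so a strong predictor would usually be left out. The second route, through potential confounders, does not define what would qualify. Neither route can pick up prior inquiry unless it has been extracted.

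What is at stake is some power in a trial sized with little to spare, and a primary analysis whose covariates are fixed only after the data are seen.

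**Working it through.** **1. The plan's own figure.** Inputs from the documents: 850 patients, 1:1, so 425 per arm; control rate 12%; difference 7 points, read as 12% against 19%; alpha 0.05. Sidedness is not stated; two-sided is assumed because it reproduces the figure (one-sided would give 88.1%).

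With pooled variance, the mean rate is 0.155 and √(2 × 0.155 × 0.845) = 0.5118. The unpooled term is √(0.12 × 0.88 + 0.19 × 0.81) = 0.5094.

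- Patients per arm for 80%: [(1.960 × 0.5118 + 0.8416 × 0.5094) / 0.07]² = 418.4, so 419 per arm or 838 in total.
- Power at 425 per arm: Φ[(0.07 × √425 − 1.960 × 0.5118) / 0.5094] = Φ(0.864) = 80.6%.

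The stated 80% is therefore the power of an unadjusted comparison, with no correlation term needed.

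**2. Inputs that the documents do not give.** Two are assumed: the share q with an inquiry before randomisation (2%, 5% or 12%), and the 12-month control rate p₁ among those patients (20% to 50%). The rate in the other controls follows from the overall 12%: p₀ = (0.12 − q·p₁)/(1 − q).

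**3. Effect of adjustment.** The correlation between prior inquiry and outcome in controls is r = (p₁ − p₀)·√[q(1 − q)] / √(0.12 × 0.88). Adjustment acts approximately like raising n per arm to n/(1 − r²).

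Example, q = 12% and p₁ = 40%: p₀ = (0.12 − 0.048)/0.88 = 0.082; r = 0.318; r² = 0.101; 425/0.899 = 473 per arm; power 84.6%.

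Example, q = 5% and p₁ = 50%: p₀ = (0.12 − 0.025)/0.95 = 0.100; r = 0.40 × 0.2179/0.3250 = 0.268; r² = 0.072; 425/0.928 = 458 per arm; power 83.4%.

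Power with adjustment at N = 850 (unadjusted 80.6%):

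| Share with prior inquiry | p₁ = 20% | 30% | 40% | 50% |
|---|---|---|---|---|
| 2% | 80.7% | 80.9% | 81.2% | 81.7% |
| 5% | 80.7% | 81.2% | 82.1% | 83.4% |
| 12% | 80.9% | 82.2% | 84.6% | 87.9% |

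**4. Check by simulation.** At 12% prevalence, 20,000 trials per scenario, comparing an unadjusted score test with a Mantel-Haenszel test stratified by prior inquiry, gave 81.0%, 82.3%, 84.9% and 88.4%. This agrees with the last row. No scenario showed a material loss of power. If nobody has a prior inquiry, the gain is zero.

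**5. If fewer patients are analysed.** Study Size Justification expects to leave about 25% out of the main analyses: 850 × 0.75 is about 638, or 319 per arm. Unadjusted power is then 68.6%. At 12% prevalence the same formula gives 69.0%, 70.5%, 73.2% and 77.4%. Adjustment does not make good that loss.

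**The case against.** **The prevalence is unknown and may be small.** A reader might take the 12% in the power paragraph as the share of participants who already have an inquiry when they enrol. The documents do not support that. The figure works there as the control outcome rate, since 12% against 19% is what returns 80.6%, and the words at baseline are not explained. Recruitment aims to reach patients early in the pathway and enrolment falls around the second evaluation day, so prior inquiries may be few. This stands, and it is why the size is given as a range that starts at zero.

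**The plan leaves a route to adjustment.** To say that the plan does not adjust would be too strong, because the screening rules could admit prior inquiry. What stands is that this is not prespecified and that no extraction of the variable is described.

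**The covariate could overlap the outcome.** The outcome window opens at the start of evaluation, while enrolment and randomisation may follow the second evaluation day (section C.1). An inquiry between those dates could be both a prior inquiry and an outcome event. This stands, and the fix has to deal with it.

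**The look-back is not entirely free.** Section D promises patients specific information about what is taken from their charts, so consent or IRB wording may need a change. That is a small cost.

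**A larger gain might be read into the 0.5.** The power paragraph gives "correlation on the same subject of 0.5". Read as a before-and-after correlation, r = 0.5 would mean 425/0.75 = 567 per arm and 90.4% power. The same sentence presents the figure as an allowance for patients clustering within sites, so the documents give no basis for that reading.

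**Conclusion.** The point holds as a cheap improvement, not as an error in the design. The primary model does not prespecify adjustment for an inquiry before randomisation, although inquiries are routinely recorded for each potential recipient and the planned form already carries dates.

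Under the assumptions above, the gain is about 0 to 3 points of power if 2-5% of patients have a prior inquiry, and about 0 to 8 points if 12% do. Both the share and the association are assumed.

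A reader might infer that the trial is throwing away a known amount of power, or that its 80% is misstated. Neither follows: the loss depends on two quantities that the documents do not report, and the 80% reproduces without adjustment. The expected 25% exclusion matters more for power than this does. The case for acting is that the cost is low, no scenario shows a material loss, and the choice can be fixed before arm-level results are seen.

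**What to change.** 1. Extend the dated extract back before randomisation, for example by 12 months, for every participant.
2. Derive prior inquiry (yes/no) strictly before the randomisation date, and count outcome inquiries only from randomisation onward, so that no event is both covariate and outcome.
3. Name prior inquiry in the Statistical Analysis Plan as a fixed covariate in the primary logistic model, whatever the baseline comparison shows.
4. Report a standardised risk difference with its confidence interval alongside the adjusted odds ratio. The odds ratio becomes conditional on prior status, whereas H₁ and the 7-point target concern proportions.
5. State what the 12% at baseline refers to.

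The cost is a wider date range in an extract already planned, a short addition to the SAP with the outcome window reworded, and possibly a change to consent or IRB wording for the look-back. No extra patients or visits are needed.
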